7.2 Trial participants and expected attendance

In total, we expect about 7400 women to be invited to the RCT, including 2200 women from Poland, 1400 from the Philippines, 1500 from Pakistan, 1300 from Arabic countries, and 500 from Somalia (Table X). Women within our five strata will be identified in the databases of BreastScreen Norway. These five strata represent the most common immigrant groups in the program. The different strata have different attendance rates, and we expect attendance rates in the control arms in the trial to be similar to those observed in 1996-2014.

Table 1. Target group 1996-2015 adapted from Bhargava et al 2018 (4), and estimated numbers for invited (total and each arm) and attended (control arm) in 2021

Country (language)	Target group 1996-2014 (n)	Expected to be invited in 2021 (n)	Attendance rate 1996-2014 (%)	Expected to attend in the control group 2021 (n)
Arabic	2600	1300 (650 in each arm)	40%	260
English	2700	1400 (700 in each arm)	54%	378
Polish	4300	2200 (1100 in each arm)	50%	550
Somali	1000	500 (250 in each arm)	14%	35
Urdu	3000	1500 (750 in each arm)	34%	255
Total	13 600	7400 (3700 in each arm)	40%	1480

Power calculations are performed for two independent sample proportions with a statistical power ($1-\beta$, where beta is the type II error rate) of 0.8 and significance level (α , type I error rate) of 0.05. To show that differences $\geq 10\%$ is statistically significant for attendance rates in the control group given in Table X, at least 356 invitations need to be sent to women from Poland, 379 to women from the Philippines, 373 to women from Pakistan, 388 to women receiving invitation in Arabic and 241 to women from Somalia (Table 2). Estimated number of invitations and sample size needed in the study arm to show that a 10% increase in the study arm compared to the control arm is statistically significant.

Table 2: Estimated number of invitations in the study arm and sample size needed in the study arm to reach statistically significant increase of 10% in attendance in the study arm (statistical power ($1-\beta$, where beta is the type II error rate) of 0.8 and significance level (α , type I error rate) of 0.05)

Stratum	Estimated number of invitations in the study arm (n)	Sample size needed in the study arm (n)
Arabic	650	388
English	700	379
Polish	1100	356
Somali*	250	241
Urdu	750	373
Total	3700	388

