Since the attendance rates and the possible number to invite differs for each stratum, we also calculated the minimal detectable differences based on expected attendance rates and invitations in the control groups (Table 3). Smaller differences for each stratum will not be considered statistically significant.

Table 3: Expected number of invitations, attendance rate, minimal detectable difference to show statistically significant difference, and estimated lowest attendance rate in the study arm that will be significantly higher than the expected rate in the control arm

Stratum	Expected number of invitations in each arm (n)	Expected attendance rate in control group	Minimal detectable difference	Lowest attendance rate in the study arm that will be significantly higher*
Arabic	650	40%	8%	48%
English	700	54%	8%	62%
Polish	1100	50%	6%	56%
Somali*	250	14%	10%	24%
Urdu	750	34%	7%	41%
Total	3700	40%	3%	43%

*Attendance rate in control group + minimal detectable difference.

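### The Polish sample size of 356 in section 7.2 and Table 2 does not follow from the protocol's own 50% control rate, which gives 388 per arm

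*Protocol*

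**What the plan says.** Section 7.2 of the protocol states the basis of the calculation: "Power calculations are performed for two independent sample proportions with a statistical power" of 0.8 and a significance level of 0.05. The effect to be detected is "a 10% increase in the study arm compared to the control arm is statistically significant".

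The text then lists one number per language group: "at least 356 invitations need to be sent to women from Poland, 379 to women from the Philippines", followed by 373 for Pakistan, 388 for the Arabic group and 241 for Somalia. It cites Table 2, which carries the same five numbers under the column heading "Sample size needed in the study arm (n"), plus 388 in the Total row.

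The Polish control rate appears twice. Table 1 expects "2200 (1100 in each arm") Polish women to be invited, with 50% attendance and 550 attenders in the control arm. The Polish row of Table 3 reads "Polish 1100 50% 6% 56", again a 50% control rate, with a 6-point detectable difference and a 56% threshold.

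**The concern.** A 10-point rise from 50% to 60% has the same binomial variances as a rise from 40% to 50%, so the two need the same sample size. Table 2 gives 388 for the Arabic stratum, whose control rate is 40%, and 356 for the Polish stratum, whose control rate is 50%. Both cannot be right on the stated inputs.

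Section 7.7 says each stratum will be analysed in its own right, so these numbers are the published justification for those analyses, and the Polish stratum is the largest. A reader who checks Table 2 against Tables 1 and 3 cannot tell which Polish input was used.

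There is also a smaller point of wording. The sentence lists the numbers as invitations to the women of each group, without saying that they are per arm. Section 4 randomises 1:1 within each language group, so both arms together need twice as many.

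**Working it through.** **Inputs.** Power 0.80, significance level 0.05 and a 10% increase come from section 7.2; the control rates from Tables 1 and 3; 1:1 allocation from section 4. The protocol does not say whether the test is two-sided or whether the 10% is absolute. Both are inferred: two-sided 0.05 with 10 percentage points reproduces every other row of Table 2, while a one-sided test or a relative 10% reproduces none.

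**Formula (per arm).** With p̄ the mean of p1 and p2, and q = 1 − p,

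n = [1.96·√(2p̄q̄) + 0.8416·√(p1q1 + p2q2)]² / (p2 − p1)²

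**Reproducing Table 2.**

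| Row | Rates | Formula | Rounded up | Stated |
|---|---|---|---|---|
| Arabic | 40% v 50% | 387.3 | 388 | 388 |
| English | 54% v 64% | 378.5 | 379 | 379 |
| Somali | 14% v 24% | 240.4 | 241 | 241 |
| Urdu | 34% v 44% | 372.3 | 373 | 373 |
| Total | 40% v 50% | 387.3 | 388 | 388 |
| **Polish** | **50% v 60%** | **387.3** | **388** | **356** |

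**Polish row in full.** p̄ = 0.55, so 2p̄q̄ = 0.495, and p1q1 + p2q2 = 0.25 + 0.24 = 0.49.

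n = [1.96 × 0.7036 + 0.8416 × 0.7000]² / 0.01 = (1.379 + 0.589)² / 0.01 = 387.3, so 388.

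The stated 356 is 32 too low (32/388 = 8.2%).

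**Could another method give 356 at 50% v 60%?** Continuity-corrected 408; unpooled variance 385; arcsine 388; one-sided 305; one-sided with continuity correction 325; one-sided unpooled 303; relative 10% increase 1565; a fall from 50% to 40%, 388. None is within 3% of 356.

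**Which control rate gives 356?** In one-point steps, only 30% and 60%. For 60% v 70%: 2p̄q̄ = 0.455 and p1q1 + p2q2 = 0.45, so n = (1.96 × 0.6745 + 0.8416 × 0.6708)² / 0.01 = 355.9.

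**Power for 50% v 60%.** Power = Φ{[0.10·√n − 1.96 × 0.7036] / 0.7000}.

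- n = 356 per arm: (1.887 − 1.379)/0.700 = 0.725, power 76.6%.
- n = 388 per arm: power 80.1%.
- n = 1100 per arm, as planned: (3.317 − 1.379)/0.700 = 2.768, power 99.7%.

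**Both arms together.** Twice the per-arm need: Poland 2 × 388 = 776, Philippines 2 × 379 = 758, Pakistan 2 × 373 = 746, Arabic 2 × 388 = 776, Somalia 2 × 241 = 482.

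**The case against.** The strongest reply is that nothing in the trial depends on the number. No one plans to stop at 356 Polish women per arm. Table 2 prints the expected 1100 next to it, and the trial's size is set by how many eligible women are invited in the year. This stands, and it limits the point to a correction of a stated figure.

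The wording point is also weaker than it may look. A reader might infer that the text asks for half the women needed, and work out powers of about 47% to 51% by treating the listed numbers as two-arm totals. The documents do not support that. The sentence cites Table 2, whose title and column heading both refer to the study arm; the Arabic group is described by the language of the letter it receives, which only the study arm gets; and no such design is proposed. Nor is the narrow Somali margin concealed: Table 2 shows 241 needed against 250 expected, in the same unit.

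Finally, a reader might infer from the back-calculation that the true Polish rate is 60%, and that the expected attenders and the overall control rate are therefore wrong. That goes too far. Two tables agree on 50%, one with 550 of 1100 and the other with a 56% threshold, against one isolated figure. Table 3's 6-point detectable difference cannot settle it, since 50% gives 5.96 points and 60% gives 5.77. The source of the rates is not available here.

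None of this rescues 356 as a result of the stated inputs.

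**Conclusion.** The Polish figure is wrong as written. On the protocol's own 50% rate the requirement is 388 per arm, and 356 would give 76.6% power where 80% is claimed. The conclusion rests on a two-sided test and an absolute 10-point effect. The protocol states neither, but the exact match of the other four strata and the Total row leaves little doubt about either.

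It would be a mistake to conclude that the Polish stratum is underpowered. The planned arm is almost three times the corrected need (1100/388 = 2.8), and every other stratum's expected arm also exceeds its per-arm need. That 356 came from a different control rate is a plausible explanation, not something the documents show.

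The missing per-arm label is a matter of clarity only.

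**What to change.** Confirm against the source data that 50% is the intended Polish attendance rate. If it is, which is what Tables 1 and 3 support, replace 356 by 388 in the text of section 7.2 and in Table 2. If a different rate was meant, keep 356 and correct the Polish rows of Tables 1 and 3 to match it.

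In the same sentence add the words per arm. The two-arm totals shown in the working could be given alongside.

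The cost is a small edit to the text and a table. The stated Polish requirement rises by 32 per arm and remains far below the number expected; no further women, data or analyses are needed.

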7.1 Statistical design

This study will be designed a superiority trial with the difference in attendance rate between the study and control arm as primary outcome. Bivariate tests will be used to analyze the primary outcome. In addition, effect estimate plots for the total effect and each specified subgroup will be made using rate ratios, corresponding 95% confidence intervals and p-values.

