7.7 Specification of subgroups

Each stratum (subgroup) will be analyzed in addition to subgroups based on background variables, meaning we will provide tests for differences and rate ratios for among other the following subgroups:

1. Arabic-speaking women defined as women born in Algeria, Egypt, Iraq, Lebanon, Morocco, Palestine, Sudan, Syria, or Tunisia
2. Polish speaking women defined as women born in Poland.
3. English speaking women defined as women born in the Philippines.
4. Urdu speaking women defined as women born in Pakistan.
5. Somali speaking women defined as women born in Somalia.
6. Age groups: <55, 55-59, 60-65 and 65+
7. Women living in Oslo.
8. Women living in the rest of Norway.

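### Protocol 7.2 uses the 80%-power detectable differences as significance cut-offs for the language strata, contradicting alpha 0.05 and the tests planned in 7.1 and 7.7

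*Protocol*

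**What the plan says.** Protocol section 7.2 sets the design parameters: "Power calculations are performed for two independent sample proportions with a statistical power" of 0.8 and a type I error rate of 0.05. Table 3 then gives, for each stratum, the number per arm, the expected control attendance, a minimal detectable difference, and the sum of the last two. The caption describes that sum as the "estimated lowest attendance rate in the study arm that will be significantly higher than the expected rate in the control arm". The text introducing the table adds a rule: "Smaller differences for each stratum will not be considered statistically significant".

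Two other sections provide for inference in the strata. Section 7.1 says that "effect estimate plots for the total effect and each specified subgroup will be made using rate ratios, corresponding 95% confidence intervals and p-values". Section 7.7 lists the five language groups first among its subgroups and says "we will provide tests for differences and rate ratios for among other the following subgroups". No section ranks the Table 3 cut-off against these tests, and none presents it as a minimal important difference or a multiplicity adjustment.

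**The concern.** A minimal detectable difference at 80% power is a true effect, about 1.96 + 0.84 = 2.80 standard errors from zero. Significance at two-sided 0.05 concerns the observed effect and needs only about 1.96 standard errors. The ratio, 1.96/2.80, is 0.70. Using the first quantity as the threshold for the second leaves a band of results that pass the planned test and fail the rule in 7.2.

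For any result in that band, the protocol gives two answers to whether the translated invitation worked in that language group. Whether the effect differs by country of birth is the secondary objective (section 3.1.2), so the conflict falls on a planned conclusion. Whoever writes the report could choose between the two rules after seeing the data.

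**Working it through.** **Inputs.** Numbers per arm, expected control rates and tabulated differences are from Protocol Table 3. Power 0.8 and alpha 0.05 are from 7.2, and 1:1 allocation is from section 4. Sidedness is not stated. Two-sided is inferred from Table 2: 40% v 50% gives 388 and 54% v 64% gives 379, both as printed, whereas one-sided gives 305 and 299.

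**Step 1: reproduce Table 3.** With control rate p, difference d, p̄ = p + d/2 and n per arm, the 80%-power difference solves

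d = 1.96·√[2p̄(1−p̄)/n] + 0.84·√{[p(1−p) + (p+d)(1−p−d)]/n}.

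Polish, n = 1100, p = 0.50: both standard errors are about 0.0213, so d ≈ 2.80 × 0.0213 = 0.060. The other strata also match Table 3 at whole percents, except that English (7.4) gives 8 only when rounded up. The tabulated values are therefore power-based.

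**Step 2: smallest observed difference with p<0.05.** With the control arm at its expected rate, solve d/√[2p̄(1−p̄)/n] = 1.96. Polish: 1.96 × 0.0213 = 0.042.

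**Step 3: effective alpha of the cut-off.** This is the two-sided probability of an observed difference at least as large as the tabulated d when both arms attend at rate p: 2·{1 − Φ(d/√[2p(1−p)/n])}. Polish: 0.06/0.02132 = 2.81, giving 0.0049.

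| Stratum | n per arm | Control | Table 3 (points) | 80%-power difference | p<0.05 reached at | Power of 0.05 test at Table 3 value | Effective alpha of cut-off |
|---|---|---|---|---|---|---|---|
| Arabic | 650 | 40% | 8 | 7.70 | 5.38 | 0.829 | 0.0032 |
| English | 700 | 54% | 8 | 7.39 | 5.19 | 0.859 | 0.0027 |
| Polish | 1100 | 50% | 6 | 5.96 | 4.18 | 0.805 | 0.0049 |
| Somali | 250 | 14% | 10 | 9.79 | 6.63 | 0.815 | 0.0013 |
| Urdu | 750 | 34% | 7 | 7.00 | 4.87 | 0.800 | 0.0042 |

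A continuity correction moves the p<0.05 thresholds only to 5.5, 5.4, 4.3, 7.2 and 5.1 points on whole counts.

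**Step 4: power if the cut-off is applied.** If the true difference equals the cut-off, the observed difference falls below it about half the time, so power is about 50%. To regain 80%, the true difference would have to be about 10.3, 10.2, 7.8, 12.9 and 9.1 points.

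**Step 5: results on which the two rules disagree.**
- Polish 605/1100 v 550/1100 (55% v 50%): z = 0.05/0.0213 = 2.35, p = 0.019; risk difference 95% CI 0.8 to 9.2 points; rate ratio 1.10 (1.02 to 1.19).
- Arabic 46% v 40%: p = 0.029.
- English 60% v 54%: p = 0.023.
- Somali 22% v 14%: p = 0.020.
- Urdu 40% v 34%: p = 0.016.

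A fixed study-arm rate can also mislead the other way once the control arm departs from expectation. Polish 56% against an observed 52% gives z = 0.04/0.02125 = 1.88, p = 0.060, although 56% is the tabulated Polish rate.

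**Step 6: Total row.** At the stated 3700 per arm and 40%, p<0.05 is reached at 2.24 points, the 80%-power difference is 3.21, and 3 points has power 0.745. The strata in Table 1 sum to 650 + 700 + 1100 + 250 + 750 = 3450 per arm and to 260 + 378 + 550 + 35 + 255 = 1478 expected control attenders, or 42.8%. On those inputs the figures are 2.34 points, 3.35 points and 0.708.

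**The case against.** The strongest reply is that this is loose wording in a planning section, meaning only that the trial is not powered for smaller stratum effects. Section 7.1 carries the statistical design, and rate ratios with confidence intervals and p-values will be shown for every stratum, so a reader could see a significant result whatever it is called. This limits the harm to mislabelling: no data are lost or biased. It does not remove the contradiction, because the sentence is a forward-looking decision rule that nothing else in the protocol withdraws.

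Three narrower points deserve weight.
- The Table 3 caption is conditional on the expected control rate. The 56% v 52% example leaves that condition, so it shows why a fixed rate cannot replace a test; it does not refute the caption. Within the condition the error is in calling the rate the lowest significant one.
- A Total difference of 3.21 or 3.35 rounds to 3 at whole percents. Even so, every stratum value is exact or rounded up, while an exact 3 points in total has only 71 to 75% power.
- The alpha range uses the null variance. An observed difference exactly at the cut-off, with pooled variance, gives p-values of about 0.002 to 0.005 instead. Either way the rule is at least about ten times stricter than 0.05.

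**Conclusion.** The concern holds. The Table 3 values are 80%-power differences, and 7.2 wrongly makes them significance thresholds for the strata. Observed differences from 5.4 to 8 points (Arabic), 5.2 to 8 (English), 4.2 to 6 (Polish), 6.6 to 10 (Somali) and 4.9 to 7 (Urdu) would pass the planned test and fail the rule.

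The figures assume two-sided testing, Table 3's numbers per arm and control arms at their expected rates. Section 1 gives an enrolment target of 14,000 against about 7400 in 7.2. A different number would move every threshold, but the conflict would remain. One-sided testing would lower the p<0.05 thresholds and widen the gap. The primary overall test is not altered; only the label on the Total row is affected. This should be fixed, as an error in how secondary results would be declared.

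**What to change.** - Delete the sentence in 7.2 that denies significance to smaller stratum differences.
- Relabel the last column of Table 3, and its caption, as the study-arm rate detectable with about 80% power given the expected control rate, or drop the column. Do not substitute other fixed thresholds: the 5.4, 5.2, 4.2, 6.6 and 4.9 points above also depend on the control rate and the numbers achieved.
- State that significance is judged by the planned test or 95% confidence interval at two-sided 0.05, using the observed rates in both arms.
- Before relabelling the Total row, reconcile its inputs with the strata. Its 80%-power difference is 3.2 points at 3700 per arm and 40%, or 3.35 at 3450 and 42.8%.

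The cost is a few lines of protocol or SAP text and one table heading. No further data or participants are needed.

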7.4 Variables of interest

The randomization variable is the country of birth, and the intervention variable is the invitation letter. In addition, we will extract the following background variables from the Cancer Registry of Norway databases for women born in the actual cohorts invited to screening in the study period: date of birth, residential address, date of immigration, country of birth, date of screening invitation, date of attendance, screening history and screening result, breast cancer.

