3.1.2 Secondary objective

To study whether the effect on attendance of inviting selected immigrant groups to BreastScreen Norway by translated invitation letters in the major official language of the woman's country of birth differs across country of birth – five language groups with a substantial number of women in the target group of the screening program will be selected. We will also stratify the outcome by age, screening history and residential time in Norway.

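### The primary comparison is fixed as unadjusted although screening history is collected; this gives away precision that matters for effects near 3 points, but it is not an error

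*Protocol*

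**What the plan says.** Section 7.4 of the protocol lists the background variables to be taken from the registry, among them "date of screening invitation, date of attendance, screening history and screening result, breast cancer". The only stated use of screening history is under the secondary objective in 3.1.2: "We will also stratify the outcome by age, screening history and residential time in Norway". Section 7.7 plans subgroups on background variables but does not list screening history by name.

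For the main comparison, section 7.1 is explicit: "Bivariate tests will be used to analyze the primary outcome". The sample-size reasoning in 7.2 has the same basis: "Power calculations are performed for two independent sample proportions", with no covariates. Table 2 is built on a 10-point increase and needs 388 women per arm for the pooled comparison. Table 1 expects "7400 (3700 in each arm" to be invited. Table 3 gives a pooled minimal detectable difference of 3 points, 40% against 43%.

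**The concern.** The endpoint is attendance at one round of a two-yearly programme. Whether a woman came last time is the same behaviour measured before she was randomised, so it is likely to be a strong predictor of whether she comes this time. It sits in registry tables that section 5.1.3 says can be linked by personal identification number, and section 7.8 expects no truly missing data.

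A test with two variables, arm and attendance, leaves that information out of the main estimate. What is at stake is the width of the confidence interval for the primary difference, and hence the chance of detecting a small real effect. Because 7.1 itself settles the method, this is a comment on a stated choice and not on something left to an unseen SAP.

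**Working it through.** **Inputs from the protocol.** 80% power and alpha 0.05 (7.2); 3,700 per arm, 40% control attendance and 3 points (Table 3, Total row); stratum sizes and attendance rates (Table 1). Sidedness is not stated. For 40% against 50%, the two-sided formula without continuity correction gives 388 per arm, the plan's own pooled figure in Table 2; one-sided it gives 305. Two-sided is therefore used.

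**Formula.** Power = Φ[(d − 1.96·SE0)/SE1], with SE0 = √[2p̄(1−p̄)/n], SE1 = √{[p1(1−p1) + p2(1−p2)]/n} and p̄ the mean of p1 and p2.

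**Unadjusted, on Table 3's inputs.** n = 3,700, 40% against 43%: SE0 = 0.011456, SE1 = 0.011450, so (0.03 − 0.022453)/0.011450 = 0.659 and power is 74.5%. The difference detectable with 80% power is 3.21 points, which matches the stated 3% only after rounding. Exactly 3 points would need 4,234 per arm.

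**Unadjusted, on the stratum rows.** The rows add to 650 + 700 + 1,100 + 250 + 750 = 3,450 per arm. Expected control attenders add to 260 + 378 + 550 + 35 + 255 = 1,478, and 1,478/3,450 = 42.8%. At 3 points, (0.03 − 0.023443)/0.011956 = 0.548 and power is 70.8%; the detectable difference is 3.35 points.

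**Larger effects, unadjusted.** At 4 points, power is 93.7% (3,700 per arm) or about 91.6% (3,450 per arm). At 10 points it exceeds 99.9% in both cases.

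**Assumed strength of screening history.** The documents give no figure, so a range is used. Take 15% of women with no earlier invitation (40% attend), 45% who did not attend last time and 40% who did. Explained variance R² is the between-category variance divided by p(1−p).

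| Attendance this round: last-time non-attenders / attenders | Between-category variance / p(1−p) | R² |
|---|---|---|
| 32% / 57% | 0.0134 / 0.2454 | 5.5% |
| 25% / 65% | 0.0341 / 0.2454 | 13.9% |
| 15% / 75% | 0.0764 / 0.2447 | 31.2% |

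**Effect of adjustment.** Approximated by an effective size n/(1−R²) in the same power formula.

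| R² | Effective n from 3,700 | Power at 3 points | Effective n from 3,450 | Power at 3 points | Detectable difference (3,450) |
|---|---|---|---|---|---|
| 0 | 3,700 | 74.5% | 3,450 | 70.8% | 3.35 |
| 5.5% | 3,914 | 77% | 3,650 | 73% | 3.26 |
| 13.9% | 4,296 | 81% | 4,006 | 77% | 3.11 |
| 31.2% | 5,378 | 88% | 5,015 | 86% | 2.78 |

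**Overlap with language group.** From Table 1's rates, the between-stratum variance is 0.01204 against p(1−p) = 0.24487, so language group alone explains about 4.9%. The table above compares adjustment for history with no adjustment at all. Attendance runs from 14% to 54% across the strata, so past attendance very probably differs by language too. The increment of history over a language-stratified analysis may therefore be smaller than the table shows.

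**The case against.** The strongest reply is that nothing here is wrong. An unadjusted two-proportion comparison in a 1:1 randomised trial is unbiased, and it matches the protocol's own power basis. This stands: the point concerns efficiency only.

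A reader might go further and infer that chance imbalance in previous attenders makes the planned result unreliable. The documents do not support that. Chance imbalance is already reflected in the unadjusted confidence interval; adjustment narrows the interval but does not repair a bias.

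A reader might also infer that pooled power is marginal overall. That is not supported either. The sample-size argument rests on 10 points, for which 388 per arm are needed and 3,700 expected. Three points is a detectable difference in Table 3, not a declared target. If the aim of 14,000 women in section 1 were met, power at 3 points with 40% control attendance would be 95.0%. The shortfall is confined to effects near 3 points at the sizes given in section 7.2.

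The size of the gain is also assumed. In the weakest scenario it is about 2 power points. In the middle one it passes 80% at 3,700 per arm but not at 3,450.

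Finally, covariate choice is often left to a SAP. That would answer an omission, but 7.1 names the primary test. A SAP could still add an adjusted analysis in support.

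**Conclusion.** The point holds as a recommendation for better precision. The protocol collects a likely strong pre-randomisation predictor, uses it only to break down results, and fixes a primary test that ignores it. The planned test remains valid.

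Under the assumed range of 5% to 31% explained variance, adjustment raises power at 3 points by about 2 to 14 percentage points at 3,700 per arm (74.5% to between 77% and 88%), and by about 2 to 15 at 3,450 (70.8% to between 73% and 86%). At 10 points it makes no practical difference. These figures rest on a two-sided 5% test, the effective-size approximation, and attendance patterns by screening history that are not in the documents. They are relative to no adjustment at all.

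**What to change.** In section 7.1, replace the sentence on bivariate tests with a primary estimate defined as the difference in attendance between arms, adjusted for:

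- language stratum;
- age;
- screening history before the trial invitation, in three levels: no earlier invitation, attended last invitation, did not attend last invitation.

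Standardise the estimate to the trial population, for example from a logistic model, so that the target remains the overall percentage-point difference. State that screening history is frozen before the trial invitation: a later extract could include the trial round itself, which is the outcome. The first level covers women invited for the first time. Report the unadjusted comparison alongside, and fix the model before final arm-level data are opened.

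The cost is a paragraph of text and a few lines of code, with no new data and no more women. The drawback is that the headline figure is model-based and no longer a raw two-by-two comparison.
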